6.4 STUDY INTERVENTION COMPLIANCE

Subjects will be instructed to take study drug daily according to the protocol and return used and unused packaging to the site at each subsequent study visit.

Compliance with administration of study drug will be assessed at each study visit during the Treatment Period and at the Early Termination Visit, if applicable, and recorded on the appropriate eCRF and the drug accountability log.

The Investigator or designee will remind subjects at each visit of the importance of following the protocol-defined schedule for taking study drug. Reasons for not following the study drug administration schedule as described in the protocol will be clearly recorded in the source documents.

Adherence will be verified through pill counts of returned bottles, phone calls and asking parents/legal guardians. Participants will be encouraged to use a cell phone or watch alarm to remind them to take the pill each day.

6.5 CONCOMITANT THERAPY

For this protocol, a prescription medication is defined as a medication that can be prescribed only by a properly authorized/licensed clinician. Medications to be reported in the Case Report Form (CRF) are concomitant prescription medications, over-the-counter medications and supplements.

6.5.1 RESCUE MEDICINE

N/A

7 STUDY INTERVENTION DISCONTINUATION AND PARTICIPANT DISCONTINUATION/WITHDRAWAL

7.1 DISCONTINUATION OF STUDY INTERVENTION

Discontinuation from gemcabene does not mean discontinuation from the study, and remaining study procedures should be completed as indicated by the study protocol. If a clinically significant finding is identified (including, but not limited to changes from baseline) after enrollment, the investigator or qualified designee will determine if any change in participant management is needed. Any new clinically relevant finding will be reported as an adverse event (AE).

The data to be collected at the time of study intervention discontinuation (Early Termination Visit) will include the following:

- Blood tests
- MRI
- Vital signs, physical measurements, and a physical examination
- Questionnaires (Food Frequency Questionnaire, PROMIS Questionnaires, Beverage Questionnaire, Physical Activity Assessment)
- Urine collection and pregnancy test (in WOCBP)
- Adverse event and concomitant medication review

7.2 PARTICIPANT DISCONTINUATION/WITHDRAWAL FROM THE STUDY

Participants are free to withdraw from participation in the study at any time upon request.

An investigator may discontinue or withdraw a participant from the study for the following reasons:

- Pregnancy
- Significant study intervention non-compliance
- If any clinical adverse event (AE), laboratory abnormality, or other medical condition or situation occurs such that continued participation in the study would not be in the best interest of the participant
- Disease progression which requires discontinuation of the study intervention

- If the participant meets an exclusion criterion (either newly developed or not previously recognized) that precludes further study participation
- Participant unable to receive gemcabene for ≥ 14 days.

The reason for participant discontinuation or withdrawal from the study will be recorded on the Case Report Form (CRF). Subjects who sign the informed consent form but do not receive the study intervention may be replaced. Subjects who sign the informed consent form, receive the study intervention for > 4 weeks, and subsequently withdraw, or are withdrawn or discontinued from the study, will not be replaced.

7.3 LOST TO FOLLOW-UP

A participant will be considered lost to follow-up if he or she fails to return for 2 scheduled visits and is unable to be contacted by the study site staff.

The following actions must be taken if a participant fails to return to the clinic for a required study visit:

- The site will attempt to contact the participant and reschedule the missed visit and counsel the participant on the importance of maintaining the assigned visit schedule and ascertain if the participant wishes to and/or should continue in the study.
- Before a participant is deemed lost to follow-up, the investigator or designee will make every effort to regain contact with the participant (where possible, 3 telephone calls and, if necessary, a certified letter to the participant's last known mailing address or local equivalent methods). These contact attempts should be documented in the participant's medical record or study file.
- Should the participant continue to be unreachable, he or she will be considered to have withdrawn from the study with a primary reason of lost to follow-up.

8 STUDY ASSESSMENTS AND PROCEDURES

8.1 EFFICACY ASSESSMENTS

Study Procedures:

Central Lab Tests

The primary and secondary outcomes listed below will be batched and measured at a central lab. At each indicated study visit (see SOA), plasma will be collected, aliquotted and frozen within 2 hours of collection and shipped to the Cardiovascular Research Lab at the Atlanta VA. After all study visits are completed and samples are obtained for all participants, the following tests will be measured:

- Lipid panel (TG, CHOL, HDLc, LDLc)
- Apolipoprotein panel (apoA-1, apoB, apoC-II, apoC-III, apoE)
- hsCRP
- Liver function panel (AST, ALT)
- Diabetes panel (GLU, INS, NEFA)
- Pharmacokinetics (Week 2, Week 6, Week 12 and in sub-study participants at Emory 0, 2, 4 and 6 hour)

Local (safety) labs

In order to assure the safety of participants at the time of their participation in the study, the labs listed below will be performed locally at the time of the visits and reviewed by the study staff. For those labs that are measured by the local lab and by the central lab (ALT, AST, Glu, Lipids) the central lab measurements will be used for outcome analysis. In the case that a central lab is missing, this will be noted and if the local lab is available it will be used. (also see SOA).

- CMP (includes Glu, BUN, Creatinine, Lytes, Calcium, Total Protein, Albumin, Alk Phos, AST, ALT, Total Bilirubin)
- CBC (includes WBC, RBC, HGB, HCT, MCV, MCH, MCHC, RDW, PLT)
- GGT
- CPK
- Lipid profile (includes cholesterol, triglycerides, HDL, LDL, and VLDL)
- HbA1c
- UA (includes chemical analysis, blood, nitrites, leukocyte esterase, protein)
- PT/INR

Imaging:

Limited MRI (no contrast) of the abdomen to measure percent hepatic steatosis and the liver multiscan. The Resonance Health (HepaFat) scan will be used for liver fat and pancreatic fat and the Perspectum Liver Multiscan (LIF and cT1 scores) will be used for inflammation and fibrosis. Body composition will be assessed by AMRA Medical AB (AMRA).

Patient reported outcomes:

PROMIS questionnaires fatigue, anxiety and depression (see Appendix B)

Study Procedures by Visit:

Please refer to Section 1.3 Schedule of Activities for additional visit details

Unscheduled Visits:

- Repeat MRI or labs
- Rescreening Visit
- Repeat ALT (for screening)
- Early Termination Visit

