5.5 STRATEGIES FOR RECRUITMENT AND RETENTION

- The target study sample size is 36 completed participants and it is expected that there will be a 33% screen fail rate and a 10% drop out rate. This will require screening approximately 60 individuals, with 40 enrolled. This will allow the study to reach the target completion of 36 participants.
- Anticipated accrual rate = 2-3 participants per site per month
- Anticipated number of sites – 3 sites
- Source of participants – Well-qualified research sites with documented expertise working with this subject population
- Potential patients will be located by chart review to look for eligibility criteria or referral by the treating physician or by reviewing lists of patients who have indicated interest in NAFLD studies
- Participant retention will be enhanced by providing age appropriate activities during the visit (movies, video games, puzzles etc.), by providing transportation assistance, by reminder phone calls and through compensation for time and travel to study visits.
- Participants will receive compensation for study participation and for transportation costs. Compensation will be based on visit length and will be dispensed to the parent/legal guardian.

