8.3.11 LONG-TERM SAFETY FOLLOW-UP

For long-term safety follow-up of subjects there will be a Week 24, Week 36, and Week 60 safety follow-up visit. The same study procedures will be conducted at all three visits, as outlined in Table 1 (Schedule of Activities). The Month 3 Safety Follow-up Visit (Week 24 Visit) will take place 12 weeks after the Week 12 or ET visit with a two week visit window. The Month 6 Safety Follow-Up Visit (Week 36 visit) will take place 24 weeks after the Week 12 or ET visit with a two week visit window. The Month 12 Safety Follow-up Visit (Week 60) will take place a year from the Week 12 or ET visit.

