9.2 SAMPLE SIZE DETERMINATION

The sample size for this study is 36 completed participants. A percent change from baseline of approximately 20% is considered to be clinically meaningful. Assuming a two-sided test at the 5% significance level, 36 completed participants will provide 81% power to detect a percent change from baseline of 20% (effect size = 0.5), if the standard deviation is 40%. Additionally, assuming a drop-out rate of 10%, a total of 40 participants is needed for enrollment into the study to ensure an adequate number of subjects complete the trial. Power was calculated using a two-sided Wilcoxon test with a 0.05 significance level using PASS v. 14.0.8 (Kaysville, UT).

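### Central ALT is assayed in one batch on frozen plasma, so each Baseline sample is stored about 12 weeks longer than its Week 12 pair, and no planned analysis would show whether that matters

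*Combined protocol and SAP*

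**What the plan says.** The primary endpoint (section 3) is each child's percent change in ALT from Baseline to Week 12. Section 9.4.2 tests it against zero, in a trial with one arm (section 4.2).

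Section 8.1 has plasma frozen within 2 hours of collection and sent to the central laboratory. On timing it says: "After all study visits are completed and samples are obtained for all participants, the following tests will be measured". ALT is in that list. The same section has ALT run locally at the time of each visit as part of the CMP, and Table 2 schedules the CMP at Baseline and Week 12. Where both results exist, "the central lab measurements will be used for outcome analysis". A local value is used only when the central one is missing.

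Sections 8.1 and 9.4 give no storage temperature or ALT stability limit for the main-study aliquots, no adjustment for storage time and no comparison of central with local ALT. They also do not require both values of a child's pair to come from the same laboratory.

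**The concern.** A single batch removes run-to-run assay drift. It does not remove the difference in age between the two samples of a pair. In every child the Baseline aliquot is the older one, so an effect of storage time on measured ALT would act in the same direction in all children. With no control arm, that effect cannot be separated from a treatment effect.

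If activity is lost in storage, Baseline is under-read more than Week 12, and a real fall looks smaller than it is. Section 9.2 treats a change of about 20% as clinically meaningful, and the rationale in section 2.1 links Week 12 falls of less than 20% to histology that did not improve. A modest distortion could therefore change how this proof-of-concept result is read.

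The fallback rule adds a second problem. A child with one central value missing gets a change score built from one fresh and one frozen result, from two laboratories.

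**Working it through.** **Step 1: the plan's own power.** Section 9.2 states: "Assuming a two-sided test at the 5% significance level", "36 completed participants will provide 81% power". The inputs are a 20% change and an SD of 40%, so d = 20/40 = 0.5.
- One-sample t-test (noncentral t), n = 36: 83.1%.
- Wilcoxon signed-rank, effective n = 36 × 3/π = 34.4: 81.2%. A simulation of 20,000 runs gives 81.5%.

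The stated 81% is reproduced.

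**Step 2: the storage gap.** Baseline is Day 1 ± 2 days and Week 12 is Day 85 ± 10 days (Table 1). The nominal gap is 85 − 1 = 84 days. The windows allow 84 ± 12, that is 72 to 96 days. The date of the batch does not change this gap.

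**Step 3: effect on a pair of central values.** Let L be the proportion of activity that the Baseline sample loses in excess of the Week 12 sample. The documents give no value for L, so it is assumed, and assumed equal in every child. For a true mean change of -20%:
- observed mean = 0.80/(1 − L) − 1
- observed SD = 40%/(1 − L)
- observed effect size = (0.20 − L)/0.40

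For example, at L = 5%: 0.80/0.95 − 1 = -15.8%; SD = 40/0.95 = 42.1%; effect size = 0.15/0.40 = 0.375.

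| L (assumed) | Observed mean | Observed SD | Effect size | Wilcoxon power |
|---|---|---|---|---|
| 0% | -20.0% | 40.0% | 0.500 | 81% |
| 1% | -19.2% | 40.4% | 0.475 | 77% |
| 3% | -17.5% | 41.2% | 0.425 | 68% |
| 5% | -15.8% | 42.1% | 0.375 | 57% |
| 10% | -11.1% | 44.4% | 0.250 | 30% |

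With no true change (t-test), the chance of a significant false fall drops from 2.5% to 0.4% at L = 5% and to 0.03% at L = 10%. The chance of a significant false rise grows from 2.5% to 10.9% and 30.8%.

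**Step 4: mixed pairs under the fallback rule.** Here the total storage loss T enters, because one value is fresh. With T = 10% (assumed) and no true change:
- Baseline local, Week 12 central: 0.90 − 1 = -10%, a false fall.
- Baseline central, Week 12 local: 1/0.90 − 1 = +11.1%, a false rise.

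**Step 5: does total storage time matter?** Section 5.5 gives "Anticipated accrual rate = 2-3 participants per site per month" and 3 sites, so 6 to 9 a month, and 40 children enrol in 40/9 = 4.4 to 40/6 = 6.7 months. The oldest Baseline sample is then 4.4 + 2.8 to 6.7 + 2.8, about 7 to 9 months old, if the batch runs after the last Week 12 visit. It is 4.4 + 13.8 to 6.7 + 13.8, about 18 to 20 months old, if the batch waits for Week 60. With a constant proportional loss r per month, the observed ratio is inflated by (1 − r)^(−2.76), where 2.76 months is the 84-day gap. Total storage time cancels.

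**The case against.** The strongest reply is that the harm is hypothetical. Nothing in the documents shows that ALT is lost in frozen plasma, and at L = 0 there is no bias. Section 10.1.10 refers to a Manual of Procedures, which may contain handling rules, and Appendix A does give storage temperatures for sub-study plasma. Single-batch central assay is also a deliberate and sensible choice. GGT (local only) and MRI steatosis are not exposed to the problem. All of this stands. It limits the point to an unverified assumption that the plan could easily check.

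Four stronger readings are tempting, and the documents do not support them.

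- *Fresh local ALT is ignored.* It is not: section 8.1 names it as the fallback. What is missing is a planned comparison.
- *The scheme could manufacture efficacy.* For a pair of central values, greater loss at Baseline hides a fall. Only a mixed pair can show a false fall, and only in the children concerned.
- *The primary result waits for Week 60, about 11 months too long.* Section 8.3.11 says "The Month 12 Safety Follow-up Visit (Week 60) will take place a year from the Week 12 or ET visit", and section 4.4 ends the study with the last scheduled visit. But the timing sentence in 8.1 also refers to samples being obtained. Central liver samples stop at Week 12 or Early Termination (Table 2), and section 4.4 defines a participant's completion as through Week 12. The wording is ambiguous.
- *Assaying earlier would cure the bias.* Under a constant rate of loss it changes nothing (Step 5). If loss slows with time, it makes the bias worse. With an assumed 10% total loss, a 3-month time constant and 6.7 months of even accrual, a true -20% averages about -17.9% if assayed at the last Week 12 visit, and about -19.9% after Week 60.

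**Conclusion.** The point holds as a conditional one. The unequal storage is certain: nominally 84 days in every child, 72 to 96 within the windows. Its effect on ALT is unknown. If loss depends on storage time, the primary estimate moves toward no fall. An assumed differential loss of 1% costs about 4 points of power and one of 10% costs about 51 (81% to 30%). These figures rest on the plan's n = 36 and SD of 40%, and on an equal proportional loss in all children. The planned analysis would not reveal such a loss. The mixing of sources under the fallback rule is a separate gap in the text, whatever the stability of ALT.

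This is a cheap improvement. It is not grounds for rejecting the central assay or for saying that the trial's result is biased.

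**What to change.** (a) In section 9.4.2, pre-specify a sensitivity analysis of the primary endpoint that uses local ALT at both Baseline and Week 12, with the same local laboratory for both values of a child's pair. Report it beside the central result. With it, examine log(central/local) against storage time. Because all samples are assayed together, storage time runs in step with collection date, so drift in a local laboratory could look like storage loss. The relation should therefore be shown by site as well as overall.

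(b) In section 8.1, state that when either central value of a child's pair is missing, local ALT is used for both visits.

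The cost is SAP and protocol wording and one extra analysis on data already scheduled; no visit or sample is added. The limitation is that local values carry between-laboratory and run-to-run variation. That is why they serve as a sensitivity analysis and do not replace the central result.

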8.2 SAFETY AND OTHER ASSESSMENTS

Specific Safety Measures:

Hemoglobin decrease

For a hemoglobin decrease of > 1.5 g/dL from baseline during the study, repeat hematology studies and reflexive evaluation of reticulocyte count will be performed. The subject's past medical history, concomitant medications (including over the counter drugs and herbal supplements), and any recent symptoms (e.g., bleeding, shortness of breath, fatigue) will be reviewed to determine a potential etiology and make a clinical assessment of the significance of the finding.

Creatinine increase

If, at any visit, a creatinine increase of > 0.3 mg/dL (27 µmol/L) from baseline, a GFR decrease of >15 mL/min from baseline is observed, a repeat chemistry/urinalysis will be performed within seven days. The subject's past medical history, concomitant medications (including over the counter drugs and herbal supplements), and any recent symptoms (e.g., fatigue, malaise, polyuria/oliguria, or palpitations) will be reviewed to determine a potential etiology and make a clinical assessment of the significance of the finding.

Possible muscle and liver injury

For muscle injury, CPK, hepatic, and renal function laboratory data will be integrated with myopathy signs and symptoms.

For liver injury, laboratory data will be integrated with hepatic signs and symptoms. Alanine aminotransferase increases > 2 × baseline with symptoms of hepatitis or > 3 × baseline with or without symptoms of hepatitis will be evaluated and managed according to guidelines for studies in patients with pre-existing liver disease. This includes a repeat assessment as soon as possible to confirm the findings and a clinical evaluation. If the participant has signs or symptoms of hepatitis or ALT > 5x baseline, the study drug will be temporarily discontinued.

Data to be provided to the participants – At a minimum, the locally run clinical labs and MRI liver fat result from baseline will be provided to each patient at the end of the study and reviewed with them by a study investigator. This includes the CMP, CBC, GGT, hemoglobin A1c, insulin, glucose and fasting lipids. The investigator may choose to share other locally run clinical labs from other time points with the participant.

8.3 ADVERSE EVENTS AND SERIOUS ADVERSE EVENTS

8.3.1 DEFINITION OF ADVERSE EVENTS (AE)

Adverse event means any untoward medical occurrence associated with the use of an intervention in humans, whether or not considered intervention-related (21 CFR 312.32 (a)).

An adverse event is defined as any untoward medical occurrence in a clinical investigation subject administered a pharmaceutical product, which does not necessarily have a causal relationship with this treatment. An adverse event can therefore be any unfavorable and/or unintended sign (including an abnormal laboratory finding), symptom, or disease temporally associated with the use of an investigational medicinal product, whether or not related to the investigational medicinal product. All adverse events, including observed or volunteered problems, complaints, or symptoms, are to be recorded on the appropriate eCRF.

Adverse events, which include abnormal and clinically significant clinical laboratory test variables, will be monitored and documented from the time of first dose of study drug (Study Day 1) until study participation is complete (the Follow-up Visit). Subjects should be instructed to report any adverse event that they experience to the Investigator. Beginning with the signing of the informed consent until the time of the first dose of study drug (Study Day 1), Investigators should make updates to medical history and record any pre-existing medical condition or signs or symptoms that changes in severity, frequency,

or seriousness in the medical history. Serious adverse events that occur prior to the first dose of study drug (Study Day 1) should be reported as an update to medical history as well as be reported on the appropriate adverse event eCRF. Beginning with the first dose of study drug (Study Day 1), Investigators should make an assessment for adverse events at each visit and record all adverse events, non-serious and serious, on the appropriate adverse event eCRF.

Wherever possible, a specific disease or syndrome rather than individual associated signs and symptoms should be identified by the Investigator and recorded on the eCRF. However, if an observed or reported sign or symptom is not considered a component of a specific disease or syndrome by the Investigator, it should be recorded as a separate adverse event on the eCRF. Additionally, the condition that led to a medical or surgical procedure (e.g., surgery, endoscopy, tooth extraction, or transfusion) should be recorded as an adverse event, not the procedure. Concomitant procedures should be recorded as such on the appropriate eCRF.

Any medical condition already present prior to the subject taking the first dose of study drug (Study Day 1) should be reported in the medical history. Any SAEs occurring prior to the first dose of study drug (Study Day 1) should be reported as an update to medical history as well as an adverse event. Any pre-existing medical condition or signs or symptoms that changes in severity, frequency, or seriousness after the subject takes the first dose of study drug (Study Day 1) and through the Follow-up Visit should be reported as an adverse event.

Clinically significant abnormal laboratory values or other examinations (e.g., ECG) that are detected at the time of the first dose of study drug (Study Day 1) and worsen during the study should be reported as adverse events. An abnormal laboratory result that is not verified by repeat testing does not necessitate reporting as an adverse event. The Investigator will exercise his or her medical, scientific, and clinical judgment in deciding whether an abnormal laboratory finding or other abnormal assessment is clinically significant. Clinically significant abnormal laboratory values occurring during the clinical study will be followed until repeat tests return to normal, stabilize, or are no longer clinically significant. Any abnormal test that is determined to be an error does not require reporting as an adverse event.

An overdose is a deliberate or inadvertent administration of a treatment at a dose higher than specified in the protocol and higher than known therapeutic doses. Overdoses with associated symptoms are always handled as AEs and reported as such. Overdoses without associated symptoms are not reported as AEs but are documented in [specify e.g., CRF] in order to collate information for the IB regarding the level of excess dosage taken or administered without adverse effects. An overdose will be reported irrespective of outcome even if toxic effects were not observed.

